8.3.1 Physical Examinations

- A complete physical examination will be performed at visits indicated in the SoA. It
 will include, at a minimum, height, weight, and assessments of the Cardiovascular,
 Respiratory, Gastrointestinal and Neurological systems.
- A symptom-based physical examination will be performed as indicated in the SoA, in a response to new symptoms, or changes in symptoms.
- Investigators should pay special attention to clinical signs related to previous serious illnesses.

21 SEP 2023 Page: 42 of 73

• Abnormal physical examination findings, including overweight/obesity when BMI >30 kg/m², are to be recorded either as medical history or as adverse events.

8.3.2 Vital Signs

- Pulse rate, and systolic and diastolic blood pressure will be assessed.
- Vital signs measurements should be preceded by at least 5 minutes of rest for the participant in a quiet setting without distractions (e.g., television, cell phones).
- Vital signs should be taken before blood collection for laboratory tests.
- Blood pressure and pulse rate measurements will be assessed once in a sitting position with a completely automated device. Manual techniques will be used only if an automated device is not available.
- In case of abnormal results, repeat measurements should be performed to adequately document potential findings, e.g. hypertension.⁶

8.3.3 Clinical Safety Laboratory Tests

- See Section 10.2 for the list of clinical laboratory tests to be performed and the SoA for the timing and frequency.
- The investigator must review the laboratory results, document this review, and record any clinically significant changes occurring during the study as an AE. The laboratory results must be retained with source documents.
- Abnormal laboratory findings associated with the underlying disease are not considered clinically significant unless judged by the investigator to be more severe than expected for the participant's condition.
- All laboratory tests with values considered clinically significantly abnormal during participation in the study or within 7 days after the last dose of study intervention should be repeated until the values return to normal or baseline or are no longer considered clinically significant by the investigator or the medical monitor.
 - If clinically significant values do not return to normal/baseline within a period of time judged reasonable by the investigator, the etiology should be identified, and the Sponsor notified.
 - All protocol-required laboratory tests, as defined in Section 10.2, must be conducted in accordance with the Laboratory manual and the SoA.
 - If laboratory values from non-protocol specified laboratory tests performed at the institution's local laboratory require a change in participant management or are considered clinically significant by the investigator (e.g., SAE or AE or dose modification), then the results must be recorded.

8.3.4 Pregnancy Testing

None of the participants of the study are women of childbearing potential. Nevertheless, a pregnancy test will be performed to confirm eligibility in all participants except those who have undergone hysterectomy and bilateral oophorectomy.

⁶ Hypertension is defined as systolic blood pressure ≥140 mmHg or diastolic blood pressure ≥90 mmHg over 3 readings on at least 2 different occasions.

21 SEP 2023 Page: 43 of 73

8.3.5 Suicidal Ideation and Behavior: Electronic Columbia-Suicide Severity Rating Scale (eC-SSRS)

Suicidal ideation and behavior will be monitored by eC-SSRS questionnaire. Use of the eC-SSRS is required by the US FDA in clinical trials of new compounds with a central mode of action.

The eC-SSRS is a fully structured participant rated questionnaire designed and developed for computer administration. Participants respond to standardized clinical questions presented in a uniform fashion and adhering to the original C-SSRS clinical conventions. The eC-SSRS assesses lifetime suicidality during an initial baseline evaluation, and then prospectively monitors ideations and behaviors at subsequent follow-up assessments. The eC-SSRS assesses the severity and frequency of suicidal ideation and behavior. The information collected in the eC-SSRS is classified into a set of 11 categories for suicidal ideation and suicidal behavior, and self-injurious behavior without suicidal intent.

See Exclusion Criteria 15 for information on when the participant should not be randomized based on suicidal behavior or ideation.

• The investigator will receive an email notification if a participant has a "Yes" score on item 4 or item 5 of the suicidal ideation section of the eC-SSRS or "Yes" on any item of the suicidal behavior section. If this happens after randomization, the participant can continue the study at the discretion of the investigator. The investigator has to report this as an adverse event. In addition, any suicidal ideation and/or behavior should be treated according to local clinical practice.

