- 13. Travel across \geq 3 time zones within 2 weeks prior to the SCR-2 visit, or planned travel across \geq 3 time zones during study.
- 14. Regular napping i.e. >3 naps per week each with duration of >30 minutes.
- 15. At screening a suicidal ideation in the past 6 months (as indicated by "Yes" on item 4 or item 5 of the suicidal ideation section of the eC-SSRS) or suicidal behavior in the past 6 months (indicated by "Yes" on any item of the suicidal behavior section of the eC-SSRS).
- 16. Clinically relevant drug or alcohol abuse within 12 months of signing of informed consent.
- 17. Use of substances that in the opinion of the investigator contribute to the participant's sleep disturbances (e.g. caffeine, alcohol, cannabis and its derivatives).
- 18. Dependent on the investigator, the contract research organisation(s) or Sponsor for education or employment (e.g. family members, employees, people who receive grants/education).
- 19. Known hypersensitivity to elinzanetant or any of the excipients in the formulation.
- 20. Inability to comply with the study procedures for any reason, including the following examples: language comprehension, psychiatric illness, general inability to get to the study site or ePRO completion.

Additional criteria

21. Current diagnosis of the following pre-malignant conditions: cervical dysplasia; breast atypia including atypical ductal hyperplasia, atypical lobular hyperplasia, lobular carcinoma in situ; cirrhosis of the liver; and nodular hepatic lesions.

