4.1.1.3 Electronic Patient Reported Outcomes (ePROs)

There are two types of missing data for ePRO measures: missing data at the 'form' level and missing data at the 'item' level.

Form level missing refers to a participant missing an entire PRO assessment for a given time point (e.g., a given day (i.e., morning and evening) for the HFDD and a given week for the PROMIS SD SF 8b). In general, form level data may be missing due to participant's early withdrawal from the study, inability to evaluate an endpoint at a particular time point, or noncompliance.

By design of the eDiary, there will be no item level missing data for the respective ePRO questionnaires because the participants have to select an answer for an item in order to move on to the next item on the eDiary/electronic handheld device, with the exception for the eC-SSRS where the form can be submitted even if incomplete.

No imputation of missing assessments will be performed for any ePRO measures.

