4.5.2 Adverse Events (AEs)

All AEs will be summarized using MedDRA (the current version at the time of analysis) PTs grouped by SOC.

Any AEs related to study procedures recorded after signing of informed consent but prior to randomization will be considered as pre-treatment AEs. AEs that occurred or worsened after the first dose of study intervention up to 14 days after the last dose of study intervention will be considered as treatment-emergent AEs (TEAEs). AEs that occurred 15 days after last dose will be considered as post-treatment AEs.

Partially missing onset AE date will be imputed following a worst-case approach as described in Section 4.1.1.4.

If the severity of a previously reported event worsens or if the relationship to study intervention/protocol required procedures changes, two separate events should be reported.

Worsening of an AE is defined as follows:

- AE intensity is worsened (e.g., moderate to severe)
- AE changed to a serious event
- AE ends with death

In case an AE starts before the date of last study intervention intake + 14 days and worsens after last study intervention intake +14 days, it will be considered as two AEs, a TEAE and a post-treatment AE.

In case of events with different intensity within a participant, the maximum reported intensity will be used. If the same event is reported as both unrelated and related to the study intervention within a participant, the event will be considered as related to study intervention. If the study intervention relationship is missing, the event will be considered as being related to the study intervention. For AEs, relationship to study intervention refers to elinzanetant and placebo only.

Overall summaries of the number of participants with pre-treatment AEs, TEAEs, and post-treatment AEs will be generated by study treatment.

The number of participants with the following AEs will be summarized by study treatment using PTs grouped by SOC:

- pre-treatment AEs
- post-treatment AEs

Version 2.0 Page: 36 of 57

- SAEs (includes both treatment-emergent and post-treatment)
- TEAEs, TEAEs of special interest, TEAEs resulting in discontinuation of study intervention, TEAEs by maximum intensity
- treatment-emergent study intervention related AEs, treatment-emergent study intervention-related AEs by maximum intensity, treatment-emergent study intervention-related AEs resulting in discontinuation of study intervention

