4.5.3.4 Electronic Columbia-Suicide Severity Rating Scale (eC-SSRS)

Suicidal ideation and behavior will be monitored by eC-SSRS questionnaire.

Version 2.0 Page: 39 of 57

The eC-SSRS assesses lifetime suicidality during an initial baseline evaluation, and then prospectively monitors ideations and behaviors at subsequent follow-up assessments. The eC-SSRS assesses the severity and frequency of suicidal ideation and behavior.

eC-SSRS outcomes will be summarized by study treatment for each visit (baseline, week 4 and 12) using descriptive statistics.

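### The eC-SSRS is summarized only visit by visit, so no per-participant count of any or worsened post-dose ideation or behavior is planned, and early-EoT and unscheduled forms have no stated place

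*Protocol*

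**What the plan says.** Protocol 8.3.5, repeated in SAP 4.5.3.4, describes two recall windows: "The eC-SSRS assesses lifetime suicidality during an initial baseline evaluation, and then prospectively monitors ideations and behaviors at subsequent follow-up assessments". The Schedule of Activities places the only pre-dose eC-SSRS at SCR-1, with later forms at Week 4 (T1) and Week 12/EoT (T3).

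The analysis is one sentence in SAP 4.5.3.4: "eC-SSRS outcomes will be summarized by study treatment for each visit (baseline, week 4 and 12) using descriptive statistics". It does not say which baseline recall is tabulated. It gives no treatment-emergent definition, no shift table and no cumulative post-dose count.

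Three other provisions bear on this:

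- Exclusion criterion 15 (Protocol 5.2) uses a second window, "At screening a suicidal ideation in the past 6 months", for ideation items 4 and 5, and the same period for any behavior item.
- Protocol 8.3.5 alerts the investigator to a Yes on "item 4 or item 5 of the suicidal ideation section of the eC-SSRS" or on any behavior item. After randomization, "The investigator has to report this as an adverse event".
- SAP 4.5.2 treats as treatment-emergent the "AEs that occurred or worsened after the first dose of study intervention up to 14 days after the last dose of study intervention", and states: "The number of participants with the following AEs will be summarized by study treatment using PTs grouped by SOC".

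On completeness, SAP 4.1.1.3 says the electronic questionnaires have no item-level gaps, "with the exception for the eC-SSRS where the form can be submitted even if incomplete". No denominator rule follows for this scale.

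**The concern.** Protocol 8.3.5 notes that the US regulator requires this instrument for new compounds acting on the central nervous system. The summary a safety reader wants from it is how many women in each arm had any ideation or behavior after dosing, and how many of them were worse than before. A by-visit table does not give that number. It counts forms at a visit, so a woman positive twice cannot be told from two women positive once, and it does not link a post-dose answer to the same woman's pre-dose answer.

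The SAP makes that link for other data. It defines treatment-emergent adverse events and laboratory abnormalities, expresses liver values relative to baseline, and plans shift tables for the PGI-S.

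With about 39 women per arm and few expected positives, the classification of one or two women is the whole result.

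**Working it through.** The documents give no rate, count or power for the eC-SSRS, so there is no plan figure to reproduce. The check sets the provisions side by side and adds simple arithmetic.

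**1. What by-visit counts identify.** With a women positive at Week 4 and b at Week 12, the number of distinct women lies between max(a, b) and a + b. The number new or worsened lies between 0 and a + b.

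| Week 4 | Week 12 | Distinct women | New or worsened |
|---|---|---|---|
| 1 | 1 | 1 to 2 | 0 to 2 |
| 2 | 2 | 2 to 4 | 0 to 4 |
| 2 | 3 | 3 to 5 | 0 to 5 |

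One woman is 1/39 = 2.6% of an arm (39 per arm from Protocol 9.5).

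**2. Which answers have a second route into a by-arm count.**

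| eC-SSRS answer after randomization | By-visit table | Mandatory AE report |
|---|---|---|
| Ideation items 4-5 | yes | yes |
| Any behavior item | yes | yes |
| Ideation items 1-3 | yes | no |

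The first two rows reach the TEAE tables when onset or worsening falls within the SAP 4.5.2 window. The third reaches them only if the investigator chooses to report it.

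**3. Which forms have a place in the table.** SAP 4.5.3.4 names baseline, Week 4 and Week 12. Schedule of Activities footnote c requires all EoT assessments at early discontinuation, which includes the eC-SSRS. SAP 4.2.1 maps an early EoT assessment to a visit for PSG only. SAP 4.1.2 keeps extra assessments at non-protocol visits in listings and out of summary tables unless stated otherwise. A woman who stops between visits, or has an unscheduled form, can therefore be absent from the summary.

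**4. The baseline column.** This step rests on assumed rates. Suppose lifetime ideation L is tabulated as baseline and each post-dose form has rate r. Expected women per arm are 39 x L and 39 x r, and the apparent change with no drug effect is r - L.

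- L = 5%, 10%, 20%: 39 x L = 2.0, 3.9, 7.8 women.
- r = 1%, 3%, 5%: 39 x r = 0.4, 1.2, 2.0 women.
- Change: from 5% - 5% = 0 to 1% - 20% = -19 percentage points. With L = 10% and r = 3% it is -7.

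With equal underlying rates this is the same in both arms, so the difference between arms at a visit is not biased.

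**5. What the first post-dose form covers.** SCR-1 is Day -42 to -24, and the Week 4 visit is Day 29 with a window of +7, so Day 29 to 36. If a follow-up form covers the time since the previous form (an assumption; the documents say only that it is prospective), its span runs from 24 + 28 = 52 days to 42 + 35 = 77 days, or 7.4 to 11 weeks. Of that, 24 to 42 days precede the first dose. A positive Week 4 form may therefore report pre-dose ideation.

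**The case against.** The strongest reply is that the important events are already counted by arm. A reader might infer from SAP 4.5.3.4 that new suicidality is never counted by arm. The documents do not support that. Week 4 and Week 12 outcomes are tabulated by treatment, and item 4-5 ideation or any behavior after randomization must be reported as an adverse event and so enters the TEAE tables. Criterion 15 strengthens this reply: women with either in the previous 6 months are excluded, so, barring an eligibility violation, any later occurrence exceeds that 6-month reference. This stands for the serious categories. It does not cover items 1-3, or worsening measured on the scale itself.

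A reader might also infer that ideation will appear to fall on elinzanetant. That needs the baseline column to hold lifetime results, which the SAP does not specify. Any such fall would be expected equally on placebo. No change from baseline is planned for this scale and no hypotheses are tested. This part of the reply stands in full.

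Two further points limit the remedy. The documents show a 6-month recall only for items 4-5 and behavior, so it cannot be assumed as a reference for items 1-3. And a count built on post-dose forms can pick up pre-dose ideation, as step 5 shows. Both are met by naming the reference and stating the caveat.

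Finally, table layouts are in a separate specification not available here, and some of this may be settled there. The baseline window and the definition of an emergent event still belong in the SAP.

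On early stoppers, SAP 6.4.1 expects no procedures after discontinuation other than the safety follow-up visit. The EoT form required by footnote c is nevertheless collected at the point of stopping and needs a home in the table.

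**Conclusion.** The point holds as a gap in the summary, at minor severity. The plan shows post-dose eC-SSRS outcomes by arm and has an adverse-event route for items 4-5 and behavior. It has no per-participant count of any or worsened post-dose ideation or behavior, no treatment-emergent count certain to include items 1-3, and no stated place for early-EoT or unscheduled forms.

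The likely size is one or two women per arm, each 2.6% of 39. The expected counts in step 4 rest on assumed rates and only illustrate the range, which starts at zero. Nothing here biases the between-arm contrast at a visit or touches the efficacy analysis. The listed safety endpoints, TEAEs and abnormal laboratory parameters, are unaffected.

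**What to change.** In SAP 4.5.3.4:

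- Label lifetime history as a row or column of its own, separate from the post-dose visits.
- Add a by-arm count of women with any post-dose ideation and with any post-dose behavior, using the worst category over all post-dose forms, including early EoT and unscheduled ones.
- Add a shift from the pre-dose category to that worst post-dose category. Use the 6-month recall as reference only where it is collected (items 4-5 and behavior), and state the reference used for items 1-3.
- Note that the first post-dose form may also cover the pre-dose screening interval.
- State how incomplete forms enter the denominator.

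The cost is SAP wording and one small extra table, with a caveat on the recall window. It uses forms already collected and changes no procedure or clinical rule.

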8.4 Adverse Events (AEs), Serious Adverse Events (SAEs) and Other Safety Reporting

The definitions of adverse events (AEs) and serious adverse events (SAEs) can be found in Section 10.3.

The definitions of device-related safety events including medical device adverse events (AE), serious adverse events (SAE), and device deficiency can be found in Section 10.6. Device deficiencies are covered in Section 8.4.7.

AEs will be reported by the participant (or, when appropriate, by a caregiver, surrogate, or the participant's legally authorized representative).

The investigator and any qualified designees are responsible for detecting, documenting, and recording events that meet the definition of an AE or SAE and remain responsible for following up all AEs (see Section 7). This includes events reported by the participant (or, when appropriate, by a caregiver, surrogate, or the participant's legally authorized representative).

The method of recording, evaluating, and assessing causality of AEs and SAEs and the procedures for completing and transmitting SAE reports are provided in Section 10.3.

8.4.1 Time Period and Frequency for Collecting AE and SAE Information

(S)AEs will be collected from the start of study intervention until the last follow-up visit at the timepoints specified in the SoA (Section 1.3). (S)AEs which are related to protocol-required study procedures (e.g., (S)AE related to invasive study procedures) will be recorded as (S)AEs from the signing of the ICF.

21 SEP 2023 Page: 44 of 73

Any medical occurrences/conditions that begin in the period between signing ICF and the start of study intervention, and which are not related to a protocol-required study procedure, will be recorded as medical history/current medical conditions, not as (S)AEs.

All SAEs will be recorded and reported to the Sponsor or designee immediately and under no circumstance should this exceed 24 hours of learning of the event, as indicated in Section 10.3. The investigator will submit any updated SAE data to the Sponsor within 24 hours of it being available.

Investigators are not obligated to actively seek information on AEs or SAEs after conclusion of the study participation. However, if the investigator learns of any SAE, including a death, at any time after a participant has been discharged from the study, and the investigator considers the event to be reasonably related to the study intervention or study participation, the investigator must promptly notify the Sponsor.

8.4.2 Method of Detecting AEs and SAEs

Care will be taken not to introduce bias when detecting AEs and/or SAEs. Open-ended and nonleading verbal questioning of the participant is the preferred method to inquire about AE occurrences.

8.4.3 Follow-up of AEs and SAEs

After the initial AE/SAE report, the investigator is required to proactively follow each participant at subsequent visits/contacts. All SAEs, and AEs of special interest (as defined in Section 8.4.6), will be followed until resolution, stabilization, the event is otherwise explained, or the participant is lost to follow-up (as defined in Section 7.3). Further information on follow-up procedures is provided in Section 10.3.

8.4.4 Regulatory Reporting Requirements for SAEs

- Prompt notification by the investigator to the Sponsor of an SAE is essential so that legal obligations and ethical responsibilities towards the safety of participants and the safety of a study intervention under clinical investigation are met.
- The Sponsor has a legal responsibility to notify both the local regulatory authority and other regulatory agencies about the safety of a study intervention under clinical investigation. The Sponsor will comply with country-specific regulatory requirements relating to safety reporting to the regulatory authority, institutional review boards (IRBs)/independent ethics committees (IECs), and investigators.
- An investigator who receives an investigator safety report describing an SAE or other specific safety information (e.g., summary or listing of SAEs) from the Sponsor will review and then file it along with the IB and will notify the IRB/IEC, if appropriate according to local requirements.
- Investigator safety reports must be prepared for suspected unexpected serious adverse reactions (SUSARs) according to local regulatory requirements and Sponsor policy and forwarded to investigators as necessary.

8.4.5 Pregnancy

In case of a suspected pregnancy, a pregnancy test should be performed. In the unlikely event of a pregnancy the following applies:

• Details of all pregnancies in participants will be collected after the start of study intervention and until end of Follow-up.

21 SEP 2023 Page: 45 of 73

- If a pregnancy is reported, the investigator will record pregnancy information on the appropriate form and submit it to the Sponsor within 24 hours of learning of the pregnancy.
- While pregnancy itself is not considered to be an AE or SAE, any pregnancy complication or elective termination of a pregnancy for medical reasons will be reported as an AE or SAE.
- Abnormal pregnancy outcomes (e.g., spontaneous abortion, fetal death, stillbirth, congenital anomalies, ectopic pregnancy) are considered SAEs, and will be reported as such.
- The participant will be followed to determine the outcome of the pregnancy. The investigator will collect follow-up information on the participant and the neonate and the information will be forwarded to the Sponsor.
- Any post-study pregnancy-related SAE considered reasonably related to the study intervention by the investigator will be reported to the Sponsor as described in Section 8.4.1 and Section 8.4.4. While the investigator is not obligated to actively seek this information in former study participants, he or she may learn of an SAE through spontaneous reporting.
- Any participant who becomes pregnant while participating in the study will permanently discontinue study intervention.

See Section 10.4 for details on collection of pregnancy information.

